12.	LITERATURE CITATIONS / REFERENCES	29
13.	PRIORITIZATION OF ANALYSES	29
14.	DATA NOT COVERED BY THIS PLAN	29
15.	APPENDICES	30
Appendix A.	Technical Detail and Supplemental Information Regarding Statistical Procedures and Programs	30
Appendix B.	Code Fragments	31
Appendix C.	Toxicity Probability Interval (TPI) Bayesian Design	32
Appendix D.	DLRM Outputs List	34

TABLE OF ABBREVIATIONS

Abbreviation/Acronym	Definition
AE	Adverse event
BQL	Lower limit of quantifications
CI	Confidence interval
cIV	Continuous intravenous
CL	Systemic clearance
C _{ss}	Steady-state drug concentration in plasma during constant-rate infusion
CSR	Clinical study report
CT	Computed tomography
CTCAE	Common terminology criteria for adverse events
DLT	Dose limiting toxicity
DMP	Data management plan
ECG	Electrocardiogram
ECOG	Eastern Cooperative Oncology Group
EOS	End of study
irCR	Immune-related Complete Response
irPD	Immune-related Progressive Disease
irRC	Immune-related Response Criteria
irSD	Immune-related Stable Disease
PK	Pharmacokinetic(s)
PKDM	Pharmacokinetics and drug metabolism
MRI	Magnetic resonance imaging
MTD	Maximum tolerated dose
PD	Progressive disease
PR	Partial response
RECIST	Response evaluation criteria in solid tumors
SAE	Serious adverse event
SAP	Statistical analysis plan
SLD	Sum of longest diameters

1. INTRODUCTION

The purpose of this statistical analysis plan (SAP) is to provide details of the statistical analyses that have been outlined within the protocol for AMG 211 Study 20130354 dated 24 March 2014. The scope of this plan includes the interim analysis and the final analysis that are planned and will be executed by the Biostatistics department or designee unless otherwise specified eg, standard PK tables may be provided by PKDM.

2. OBJECTIVES

2.1 Primary Objectives

- Evaluate the safety and tolerability of AMG 211 in adult subjects with relapsed/refractory GI adenocarcinomas
- Determine the maximum tolerated dose (MTD) and/or biologically active dose (eg, recommended phase 2 dose)

2.2 Secondary Objectives

- Describe the pharmacokinetics (PK) of AMG 211
- Determine the formation of anti-AMG 211 antibodies
- Evaluate time to progression and to evaluate the proportion of subjects progression-free at 6 months
- Evaluate the anti-tumor activity of AMG 211 by evaluating
 - The number and proportion of subjects with objective response according to the modified Immune-related Response Criteria (irRC)
 - The duration of response and time to response

2.3 Exploratory Objectives

- Evaluate the protein, nucleic acid, and cellular biomarkers in blood (eg, cytokines, lymphocyte subsets) before and following treatment with AMG 211
- Evaluate the effects of genetic variations in cancer genes and multiple other aspects of the tumor and tumor microenvironment before and following treatment with AMG 211 which may include CEA expression, markers of necrosis or apoptosis, and potential changes in the nature and number of tumor infiltrating lymphocytes

3. STUDY OVERVIEW

3.1 Study Design

This is a multi-center, open-label, sequential dose-escalation study evaluating AMG 211 as a cIV infusion in adult subjects who have relapsed/refractory GI adenocarcinoma. Table 1 presents an overview of the study design. Additional details follow below.

Table 1. Study Design Overview

Part	Cohort	Dose Level	Number of Subjects
Dose Escalation	1	200 µg/d for 7 days in cycle 1 200 µg/d for 14 days in cycle 2 and all subsequent cycles	3-6
	2	200 µg/d for 14 days in all cycles	3-6
	3	400 µg/d for 14 days in all cycles	3-6
	4	800 µg/d for 14 days in all cycles	3-6
	5	1600 µg/d for 14 days in all cycles	3-6
	6	3200 µg/d for 14 days in all cycles	3-6
	7	6400 µg/d for 14 days in all cycles	3-6
28-day Schedule	X-1	Dose Level -1 of 14-day Schedule × 28 days	3-6
	X-2	MTD × 28 days	3-6
Dose Expansion	A	MTD or Highest Tested Dose	10

Abbreviations: d = day; DLT = dose-limiting toxicity; DRLM = dose level review meeting; EC50 = 50% of the maximal effective concentration level; MTD = maximum tolerated dose; PD = pharmacodynamic; PK = pharmacokinetic.

^a Alternative dosing regimens (eg, 28-day infusions) may be explored after a DLRM decision based on 1) occurrence of DLT(s) or other emerging safety data; 2) PK/PD data demonstrating drug exposure that is in the range or above the mean EC50 concentration of 29 ng/mL; 3) absence of objective responses in the 14-day infusion schedule.

In the dose-escalation cohorts, subjects will be assigned sequentially into cohorts as they open. Three subjects will initially be enrolled into each dose-escalation cohort with at least a 48-hour interval between treatment of subject 1 and subject 2 of each cohort. In the event that a DLT is observed, additional subjects may be enrolled for a total of up to 6 evaluable subjects.

The dose-expansion cohort will be initiated after completion of the dose-escalation cohorts. Up to 10 subjects will be enrolled and treated at the dose level determined in the dose-escalation cohorts.

Subjects will be treated with AMG 211 until confirmed disease progression per modified irRC (Appendix D in the protocol), or intolerance of study treatment, or clinically significant deterioration of health status requiring discontinuation, whichever occurs first. Due to the mechanism of action of immune-enhancing therapies, subjects may experience an apparent enlargement of existing lesions or the appearance of new lesions prior to maximal clinical benefit of AMG 211.

For the schedule of assessment, please refer to section 7.1 in the protocol.

3.1.1 Dose Escalation Phase

The dose-escalation part of the study is aimed at determining the MTD, safety, tolerability, PK, and PD of AMG 211. Planned dose levels for the dose-escalation cohorts are as follows: 200, 400, 800, 1600, 3200, and 6400 µg/d. Alternative dose levels may be explored based on emerging data.

Subjects in cohort 1 of the dose-escalation cohorts will receive AMG 211 for 7 days followed by 21 days off treatment (cycle 1). After completing cycle 1, if no DLTs are observed, all subjects in cohort 1 will be allowed to continue treatment with the same dose of AMG 211, but the infusion duration will be 14 days followed by 14 days off treatment.

In the subsequent dose-escalation cohorts, AMG 211 will be administered at escalating doses in a 2 weeks on and 2 weeks off schedule. Based on the results, the Dose Level Review Team (DLRT) may choose to extend the infusion duration from 14 to 28 days (a 4 weeks on and 2 weeks off schedule) if the 14-day administration schedule has been well tolerated and the safety profile allows for a longer infusion duration, and no anti-tumor response has been observed in the 14-day administration schedule.

Moreover, the DLRT may decide to enroll in parallel into a cohort with a 28-day treatment duration or to prioritize one infusion schedule.

Dose escalation decisions will consider the incidence of DLTs among DLT-evaluable subjects that occur during the first 28 days of treatment. For definition of DLT-evaluable subjects, please refer to section 3.4 in the protocol.

A safety review of dose escalation is planned after all subjects in dose escalation have had the opportunity to complete 6 months of the treatment.

3.1.1.1 Dose Escalation and Dose Stopping Rules

Escalation to a higher dose cohort will only proceed when the previous dose(s) has (have) been found to be reasonably tolerated based on available study data through the DLT period for all DLT-evaluable subjects enrolled within a cohort and upon unanimous decision of the DLRM members. Dosing changes will be made on a treatment cohort basis and a case-by-case basis. Dose schedule changes will be made on a case-by-case basis. Dose decisions are planned after every 3 to 6 DLT-evaluable subjects are enrolled throughout the dose-escalation cohorts. Decisions made during the meeting will be documented in a dose level review memo.

The DLRT considers the recommendation for subsequent doses based on the following rules:

- Based on the modified TPI Bayesian model, the next dose is the one with the highest probability of the target TPI (0.20, 0.35), but with a less than 0.25 probability of an excessive or unacceptable TPI.
- If ≥ 1 subject has a DLT at a dose level, then dose escalation cannot occur unless there are 6 or more DLT-evaluable subjects at that dose level. However, if a transient cytokine-release syndrome is reported as the DLT, but resolves within 48 hours and can be managed with prophylactic corticosteroids, the DLRT may decide to escalate the dose with the institution of prophylactic corticosteroid administration.
- The maximum allowed dose increase will be 1 dose level above the maximum of previous evaluated doses.
- Dose escalation can be achieved by evaluating a higher dose level with the same infusion duration (eg, 800 μ g/day for 14 days to 1600 μ g/day for 14 days), or by evaluating the same dose level with a prolonged infusion duration (eg, from 800 μ g/day for 14 days to 800 μ g/day for 28 days). The DLRT may also decide to explore in parallel both options mentioned above after the dose-escalation decision is made, or to prioritize one schedule. In this case, 2 TPI models may be run in parallel to obtain dose recommendations for these 2 schedules separately.
- Intermediate dose levels not pre-specified may be considered based on the optimal dose recommended by the TPI model.

The DLRT is responsible for making the decision to end dose escalation. The DLRT may consider the modeling of dose escalation complete if 1 of the following rules is met:

- The highest planned dose level is evaluated and no DLTs occur at any dose level. In this case the maximum administered dose will be used in a dose-expansion cohort.
- The TPI Bayesian model recommends the same dose 3 times (not necessarily sequentially).

- A total of approximately 24 DLT-evaluable subjects have been enrolled.

3.1.2 Dose Expansion Phase

[figure not shown]
At the completion of the dose-escalation cohorts, additional subjects (up to 10) will be enrolled into a dose-expansion cohort to gain further clinical experience with AMG 211.

The dose to be evaluated will be at or below the MTD from the dose-escalation cohorts.

A final estimate of the recommended phase 2 dose will be based on the toxicity probability interval (TPI) Bayesian model using all DLT-evaluable subjects.

See Section 3 of the protocol for further details.

3.1.3 Study Schema

cIV = continuous intravenous; d = day; DLRT = dose level review team; DLT = dose-limiting toxicity; MTD = maximum tolerated dose; TPI = toxicity probability interval

3.2 Sample Size

It is anticipated that up to 34 subjects will be enrolled in this study. Approximately 24 subjects will be enrolled in the dose-escalation cohorts and up to 10 subjects will be enrolled in the dose-expansion cohort.

The sample size in dose-escalation cohort is determined empirically and is consistent with this type of study using a modified TPI Bayesian model design ([Bailey et al, 2009](#); [Neuenschwander et al, 2008](#)).

Refer to Appendix E in the protocol for details of the modified TPI Bayesian model, the average sample size, and other design operating characteristics.

In the dose-escalation cohorts, with 3 DLT-evaluable subjects per dose level, there is a 49% to 73% probability of observing at least 1 DLT if the true DLT rate is 20% to 35%.

In the dose-expansion cohort, an exact 80% binomial confidence interval (CI) will be provided for the ORR. With 10 subjects and 20% ORR, the expected 80% CI and its half-width would be 5.4% to 45.0% and 19.8%, respectively. In this case, the probability of observing at least 1 ORR among 10 subjects is 89.2% and the probability of observing at least 2 ORRs is 62.4%.

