10.2 Sample Size Considerations

It is anticipated that approximately 78 subjects will be enrolled in this study.

Approximately 39 subjects will be enrolled in the dose-escalation cohorts and approximately 39 subjects will be enrolled in the dose-expansion cohorts.

The sample size in dose-escalation cohort is determined empirically and is consistent with this type of study using a modified TPI Bayesian model design (Bailey et al, 2009; Neuenschwander et al, 2008).

Refer to [Appendix E](#) for details of the modified TPI Bayesian model, the average sample size, and other design operating characteristics.

In the dose-escalation cohorts, with 3 DLT-evaluable subjects per dose level, there is a 49% to 73% probability of observing at least 1 DLT if the true DLT rate is 20% to 35%.

In the dose-expansion cohorts, with 39 subjects there is a 86% probability of observing at least one adverse event with 5% incidence rate. In the dose-expansion cohorts, an exact 80% binomial confidence interval (CI) will be provided for the ORR. With 39 subjects and 20.5% ORR, the expected 80% CI and its half-width would be 12.3% to 31.2% and 9.5%, respectively.

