10.3.1 Interim Analyses

The DLRT (see [Section 10.3.2](#)) is responsible for all dose level decisions during dose escalation. Dose decisions are planned after every 3 to 6 subjects are enrolled throughout the dose-escalation cohorts. The DLRT considers the recommendation for subsequent doses based on the following rules:

- Based on the modified TPI Bayesian model, the next dose is the one with the highest probability of the target TPI (0.20, 0.35), but with a less than 0.25 probability of an excessive or unacceptable TPI.
- If ≥ 1 subject has a DLT at a dose level, then dose escalation cannot occur unless there are 6 or more DLT-evaluable subjects at that dose level. However, if a transient cytokine-release syndrome is reported as the DLT, but resolves within

48 hours and can be managed with prophylactic corticosteroids, the DLRT may decide to escalate the dose with the institution of prophylactic corticosteroid administration.

- The maximum allowed dose increase will be 1 dose level above the maximum of previous evaluated doses.
- Dose escalation can be achieved by evaluating a higher dose level with the same infusion duration (eg, 800 µg/day for 14 days to 1600 µg/day for 14 days), or by evaluating the same dose level with a prolonged infusion duration (eg, from 800 µg/day for 14 days to 800 µg/day for 28 days). The DLRT may also decide to explore in parallel both options mentioned above after the dose-escalation decision is made, or to prioritize one schedule. In this case, 2 TPI models may be run in parallel to obtain dose recommendations for these 2 schedules separately.
- Intermediate dose levels not pre-specified may be considered based on the optimal dose recommended by the TPI model.

The DLRT is responsible for making the decision to end dose escalation. Generally, the DLRT may consider the dose escalation complete if 1 of the following rules is met:

- The highest planned dose level is evaluated and no DLTs occur at any dose level. In this case the maximum administered dose will be used in a dose-expansion cohort.
- The TPI Bayesian model recommends the same dose 3 times (not necessarily sequentially).
- A total of approximately 39 DLT-evaluable subjects have been enrolled.

The Amgen Medical Monitor and Amgen Global Safety Officer can make dose decisions without convening the DRLT in the following limited circumstances:

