10.9 Changes from Protocol-Specified Analyses

There are no changes to the protocol-specified analyses.

11. LIST OF PLANNED TABLES, FIGURES AND LISTINGS [TFLs]

The definitive list of TFLs to be produced for this study is documented in the Programme Index.

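### The supplied SAP was not brought up to the current protocol: it plans 34 subjects, a completion criterion of 24 and an expansion of 10, against 78, 39 and 39

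*SAP*

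**What the plan says.** **SAP.** Section 3.2 opens with "It is anticipated that up to 34 subjects will be enrolled in this study" and continues: "Approximately 24 subjects will be enrolled in the dose-escalation cohorts and up to 10 subjects will be enrolled in the dose-expansion cohort". Section 3.1.2 repeats the expansion size: "additional subjects (up to 10) will be enrolled into a dose-expansion cohort to gain further clinical experience with AMG 211". Table 1 in 3.1 also shows 10. One of the conditions in 3.1.1.1 under which the dose level review team can regard escalation modelling as finished is "A total of approximately 24 DLT-evaluable subjects have been enrolled"; section 8 carries the same line. Planning precision for ORR in 3.2 assumes 10 subjects and a 20% rate: exact 80% interval 5.4% to 45.0%, half-width 19.8 points. Section 7.1 analyses escalation subjects by the dose they first received, but expansion subjects by the one dose chosen for that part.

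**Protocol.** Section 10.2 says "It is anticipated that approximately 78 subjects will be enrolled in this study", about 39 in each part. The matching completion condition in 10.3.1 is "A total of approximately 39 DLT-evaluable subjects have been enrolled". Section 3.1 has the expansion run at multiple dose levels. About 29 of its 39 subjects also join the Imaging Study; they may start while escalation is open and may receive less than the MTD. ORR precision in 10.2 assumes 39 subjects and a 20.5% rate: 12.3% to 31.2%, half-width 9.5 points.

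**How they are linked.** SAP section 1 says it details the analyses "outlined within the protocol for AMG 211 Study 20130354 dated 24 March 2014", and SAP 10.9 states "There are no changes to the protocol-specified analyses". The protocol's amendment history shows the total rising from 34 to 78 in Amendment 2 (3 September 2015). The current text is Amendment 3 (10 May 2016).

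**The concern.** The two documents should describe one design, and here they describe two. The completion criterion belongs to the MTD work, which is a primary objective, so a reader holding both documents finds two thresholds for the same decision. The expansion differs in structure as well as size: a single dose after escalation in the SAP, several doses partly in parallel with escalation in the protocol.

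That structural difference reaches the analysis. The by-dose safety tables report the primary endpoint, and SAP 7.1 gives no workable way to place an expansion subject in a dose group once there is more than one expansion dose. The SAP also never mentions the Imaging Study, although the protocol treats those expansion subjects differently when estimating the MTD.

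**Working it through.** **1. The SAP's own figures (n=10, 20%, so 2 responders).** The Clopper-Pearson 80% limits are the 0.10 quantile of Beta(x, n−x+1) and the 0.90 quantile of Beta(x+1, n−x).
- Lower limit, Beta(2, 9): 5.45%. Upper limit, Beta(3, 8): 44.96%. Half-width 19.75 points. Stated: 5.4%, 45.0%, 19.8.
- P(at least 1 response) = 1 − 0.8^10 = 89.26% (stated 89.2%).
- P(at least 2) = 1 − 0.8^10 − 10 × 0.2 × 0.8^9 = 62.42% (stated 62.4%).

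All agree to within 0.1 point. The SAP's sums are right for its inputs.

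**2. The protocol's figures (n=39, 8 responders, 8/39 = 20.5%).**
- Lower limit, Beta(8, 32): 12.33%. Upper limit, Beta(9, 31): 31.18%. Half-width 9.42 points. The stated 9.5 follows from the rounded limits: (31.2 − 12.3)/2 = 9.45.
- P(at least one adverse event of 5% incidence) = 1 − 0.95^39 = 86.5% (stated 86%). With the SAP's 10 subjects it would be 1 − 0.95^10 = 40.1%.

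**3. Shared figure.** For 3 subjects at a DLT rate of 20% to 35%: 1 − 0.8^3 = 48.8% and 1 − 0.65^3 = 72.5%. Both documents state 49% to 73%, and the drift does not affect this.

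**4. Side by side.**

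| Item | SAP | Protocol | Difference |
|---|---|---|---|
| Total subjects | up to 34 | about 78 | 44 |
| DLT-evaluable subjects for completion | about 24 | about 39 | 15 |
| Expansion subjects | up to 10 | about 39 | 29 |
| Expansion doses | one | several | – |
| Highest dose level named (µg/day) | 6400 | up to 12800 | – |
| ORR half-width (points) | 19.8 | 9.5 | about half |

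**5. Which n the ORR interval will have.** Protocol 10.4.3.3 and SAP 10.6.2 both tabulate ORR for subjects treated at the MTD. Of the 39 expansion subjects, 39 − 29 = 10 are outside the Imaging Study and are to receive the MTD or recommended phase 2 dose. If those two doses coincide (an assumption), the expansion part contributes between about 10 and 39 subjects. At an ORR near 20%, the half-width then runs from 19.8 down to 9.4 points. Copying the n=39 figure into the SAP would therefore state the best case only.

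**6. Population for the final MTD estimate.** The MTD definition in SAP section 6 uses DLT-evaluable subjects from escalation and expansion. Protocol 3.1 uses the same pooled population for the recommended phase 2 dose. Protocol 10.4.2 uses escalation subjects only, excludes Imaging Study expansion subjects, and adds a sensitivity analysis over both parts that the SAP lacks.

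**The case against.** The strongest reply is that little follows in practice. The rule that selects the dose is identical in both documents: target interval 0.20 to 0.35, overdose probability below 0.25, six evaluable subjects after a DLT, and a one-level cap on increases. Only a soft size limit differs, and the protocol carries the current one. The n=10 precision is planning text, and the reported interval will use the actual n with the same exact method. All of this stands, and it limits the consequence.

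Three stronger readings are tempting and are not supported.

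- **That the SAP, if followed, would have closed escalation modelling before the 12800 µg/day level.** The criterion is approximate and allows the review team to stop without obliging it to. Protocol 2.2.4 reports about 32 subjects treated by April 2016, but not how many were DLT-evaluable or in escalation. SAP 3.1.1 already allows alternative dose levels. Both documents also allow completion once the highest planned level is evaluated with no DLT anywhere.
- **That SAP 10.9 is a false declaration.** The SAP names the March 2014 protocol, and on these figures nothing supplied shows that it departed from that version. The statement is out of date.
- **That the SAP contains a calculation error.** It does not (step 1).

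It is also fair to say that the SAP's own date is not visible in the supplied copy, so whether a later SAP exists cannot be checked.

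The reply does not dispose of the dose-assignment rule in SAP 7.1, which cannot be carried out for a multi-dose expansion, or of the unresolved MTD population.

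**Conclusion.** The point holds as a failure of alignment in the supplied SAP. Total size, completion criterion and expansion size are 34, 24 and 10 in the SAP against 78, 39 and 39 in the protocol, and the planned ORR half-width differs by a factor of about two. No dose decision is shown to have been changed by this. The part that bears directly on analysis is SAP 7.1, which has no defined dose group for expansion subjects under the current design; next is the conflict over who enters the final MTD estimate, where the protocol also disagrees with itself.

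This rests on the supplied SAP being the one in force, and on the current protocol text rather than on the amendment log, which only explains where the gap came from.

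**What to change.** Amend the SAP to the current protocol before the primary analysis:

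- Update the sample sizes and completion criterion in 3.1 (including Table 1), 3.1.1.1, 3.1.2, 3.2 and 8.
- Change 7.1 so that expansion subjects, like escalation subjects, are analysed by the dose they initially received.
- Replace the n=10 precision text in 3.2 with precision for MTD-treated subjects. Give n=39 as the upper case, reached only if all expansion subjects are treated at the MTD, and say whether escalation subjects at that dose are counted.
- Reconcile the dose-level text with the protocol. The model appendices in both documents still anchor the prior at 6400 µg/day, so changing the dose list alone will not settle the reference dose.
- Reconcile the population for the final MTD estimate across SAP section 6, protocol 3.1 and protocol 10.4.2, and carry the protocol's sensitivity analysis into the SAP.
- Update the protocol version in section 1 and the statement in 10.9.

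The cost is a SAP amendment, plus a protocol clarification on the MTD population. No new subjects or data are needed.
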